8.3.3.3 EXPECTEDNESS

It is possible that participants could report musculoskeletal complications and/or cardiopulmonary complications that have been associated with vigorous bouts of physical activity. However, the intervention will not prescribe vigorous intensity activity, rather walking at a low to moderate intensity will be encouraged.

8.3.4 TIME PERIOD AND FREQUENCY FOR EVENT ASSESSMENT AND FOLLOW-UP

Our team will continually be monitoring participant's progress in the study. Participants will be advised to contact our team by phone or email immediately if they experience an adverse event. Our team will be checking our email and voicemail daily.

8.3.5 ADVERSE EVENT REPORTING

Any adverse events reported to our team by participants will be reported to the Human Subjects Office within 10 working days by the principal investigator ([name]). We will follow the Human Subjects Office policy for reporting adverse events

8.3.6 SERIOUS ADVERSE EVENT REPORTING

Any adverse events reported to our team by participants will be reported to the Human Subjects Office immediately by the principal investigator ([name]). We will follow the Human Subjects Office policy for reporting adverse events

8.3.7 REPORTING EVENTS TO PARTICIPANTS

We will report any significant events that may impact their willingness to participate to participants as we learn of them.

8.3.8 EVENTS OF SPECIAL INTEREST

N/A

8.3.9 REPORTING OF PREGNANCY

Pregnancy is an exclusion criteria for this study. We will not be reporting pregnancy.

8.4 UNANTICIPATED PROBLEMS

- 8.4.1 DEFINITION OF UNANTICIPATED PROBLEMS
- 8.4.2 UNANTICIPATED PROBLEMS REPORTING
- 8.4.3 REPORTING UNANTICIPATED PROBLEMS TO PARTICIPANTS

9 STATISTICAL CONSIDERATIONS

9.1 STATISTICAL HYPOTHESES

- Primary Efficacy Endpoint(s): We hypothesize that participants will increase their average steps/day from
 baseline to the initial adoption of the active intervention, there will be a significant difference in average
 steps/day from baseline to the last week of the active intervention, there will be a significant difference in
 average steps/day from baseline to the follow-up phase post-active intervention, participants will
 experience a decrease in average steps/day each day from the start of the 8-week intervention to the
 end. two to week eight.
- Secondary Efficacy Endpoint(s): We hypothesize participants will increase their feelings of social support, self-efficacy, and outcome expectations, and decrease their feeling of social isolation from baseline to post-active intervention. We hypothesize this will be an acceptable multilevel mHealth intervention among older adults living in a retirement community.

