Endpoints*: Primary Endpoint: 8-week active intervention (August 26,

2019)

Secondary 4-week follow up (September 22, 2019)

Endpoints:

Study Population: Adults (25-64 years) and older adults (65+ years)

Phase* or Stage:

Description of Sites/Facilities One retirement community **Enrolling Participants:**

Description of Study Intervention/Experimental Manipulation: All participants will then be provided with a Fitbit activity monitor and instructed to wear it 24 hours/day (except for bathing/swimming time) for the next 4 days. After 4 days of baseline data collection, our team will assign participants to one of three teams through randomization based on their baseline activity data. The three teams will be identified by three colors of wrist bands that hold the Fitbit monitor; black white and teal.

After baseline data collection, the research team will hold a kick-off event for the participants. The research team will give a brief presentation describing the study again. Participants will be informed of their team by a research team member and will be provided a wrist band that corresponds to their team color (black, white or teal). At that point, participants will receive written instructions ("game rules") on how to play the MapTrek intervention (our virtual walking race platform).

[figure not shown]
As part of the MapTrek game, participants will be asked to wear their Fitbit activity monitor every day for 12 weeks. For the first eight weeks, participants will participate in four team based walking races, each two weeks long. Participants will view their team progress on TV monitors placed in various locations at the Oaknoll facility. The Oaknoll leadership has given us approval to do this at their facility (see letter of support). The monitors will present aggregated team data and will not report any individual data that could link back to the individual participant. After the 8-week active intervention, we will take MapTrek away and will ask participants to wear the Fitbit for an additional 4 weeks. This will be done to determine the effects of MapTrek had on physical activity compared to a control where participants only wear the Fitbit.

Study Duration*: 12 weeks

Participant Duration: 13 weeks

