3 OBJECTIVES AND ENDPOINTS

OBJECTIVES	ENDPOINTS	JUSTIFICATION FOR ENDPOINTS	PUTATIVE MECHANISMS OF ACTION
Primary			
1. To determine the efficacy of MapTrek for improving physical activity levels of older adults living in a residential facility.	Assessments made at baseline, 8 weeks and 12 weeks.	We will determine whether the intervention was effective at 8 weeks and whether participants maintained outcomes at 12 weeks.	
Secondary			
1. To determine the efficacy of MapTrek for improving psychosocial outcomes(e.g., self-efficacy, social support, outcome expectations) among older adults living in a residential facility.		We will determine whether the intervention was effective at 8 weeks and whether participants maintained outcomes at 12 weeks.	
2. To determine the acceptability of MapTrek among older adults living in a residential facility.	We will assess acceptability at 8 weeks.	Participants will have just finished the intervention at 8 weeks.	
Tertiary/Exploratory			

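### Section 9.1 makes four step-count hypotheses primary with no ranking or multiplicity rule, in conflict with 1.1, and the baseline window and analysis set for the primary contrast are not fixed

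*Combined protocol and SAP*

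**What the plan says.** **Hypotheses.** Section 9.1 lists four under its primary efficacy heading:

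1. A rise in steps from baseline to initial adoption, whose days are not stated.
2. A significant difference in "steps/day from baseline to the last week of the active intervention, there will be a significant difference in" the next contrast.
3. That next contrast: "average steps/day from baseline to the follow-up phase post-active intervention, participants will" (the last two words open hypothesis 4).
4. A daily decline across the intervention. The sentence closes with the fragment "end. two to week eight".

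Sections 9.4.1 and 9.4.2 add no ranking, success rule or allocation of the significance level. Section 9.4.2 is one broken sentence that names both mixed models and repeated-measures ANOVA.

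**Endpoints.** Section 1.1 gives "Primary Endpoint: 8-week active intervention" and lists "4-week follow up (September 22, 2019") as secondary. Section 3 has "Assessments made at baseline, 8 weeks and 12 weeks" against the primary objective, but its justification judges effectiveness at 8 weeks and maintenance at 12. Section 1.1 also says the follow-up weeks serve to assess MapTrek "compared to a control where participants only wear the Fitbit". That comparison is not among the hypotheses in 9.1.

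**Baseline.** Section 1.1 says "After 4 days of baseline data collection, our team will assign participants to one of three teams" and puts the kick-off event after baseline. Section 6.1.1 describes a two-week baseline with the kick-off inside it.

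**Population.** The objectives and 9.2 concern older adults. Section 6.1.1 enrols residents and employees, 5.5 expects 75 older adults and 25 other adults, and 9.3 is a heading without text.

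**The concern.** A reader cannot tell which comparison decides whether MapTrek worked. Follow-up is primary in one place and secondary in another. The last-week and follow-up hypotheses have no direction, although the objective is improvement. The fourth predicts a fall in steps, so confirming it cannot show efficacy.

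This matters more than usual here because the contrasts are expected to differ. Section 4.2 reports that in the prior trial steps rose at once and then decayed towards baseline. A good early result and a weak last-week result are therefore plausible together, and the plan lets either be presented as the primary finding. Ranking the hypotheses would not settle this alone: the same contrast can still be computed from two baseline windows, with or without employees.

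**Working it through.** **1. What the sample size covers.** Section 9.2 gives a difference of 1,750 steps, an SD of 2,000, a level of 0.05, 80% power and 42 participants. The two-independent-group formula gives n per group = 2 x (2,000/1,750)² x (1.960 + 0.842)² = 20.5, so 21 per group and 42 in total. The plan's figure is reproduced with a two-sided 0.05; a one-sided test would give 17 per group, or 34. So 9.2 spends the whole 0.05 on one contrast. Whether a two-group formula suits a pre-post design is a separate question.

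**2. Status of each comparison.**

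| Comparison | 1.1 | 3 | 9.1 | 9.2 |
|---|---|---|---|---|
| Initial adoption vs baseline | not named | not named | primary | – |
| Last active week vs baseline | fits the 8-week primary | 8 weeks, effectiveness | primary | fits pre-post |
| Follow-up vs baseline | secondary | primary row, as maintenance | primary | – |
| Daily decline | not named | not named | primary | – |
| Active vs Fitbit-only weeks | stated purpose of follow-up | not named | absent | – |

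**3. False-claim rate.** Take the three baseline contrasts, each tested at two-sided 0.05, with a claim made if any shows a significant increase. The decline is left out because it is not an efficacy claim. One such test has a false-claim rate of 0.05/2 = 2.5%. For k contrasts with no true change and equal correlation r:

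P(any Z > 1.96) = 1 − ∫ φ(x) · Φ((1.96 − √r·x)/√(1 − r))^k dx

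| Contrasts | r = 0 | r = 0.5 | r = 0.9 |
|---|---|---|---|
| Two (early, last week) | 4.9% | 4.5% | 3.5% |
| Three (plus follow-up) | 7.3% | 6.3% | 4.2% |

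At r = 0 the entries are 1 − 0.975² and 1 − 0.975³. The value r = 0.5 arises when contrasts share a baseline and all period means are equally variable and independent. Whatever the correlation, three contrasts cannot exceed 3 x 2.5% = 7.5%.

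**4. Can the early and last-week contrasts disagree?** Section 4.2 gives a decay of 44.8 steps/day in the prior MapTrek group. If that held linearly here, mid-week 1 to mid-week 8 is 49 days, and 44.8 x 49 = 2,195 steps/day, more than the 1,750 in 9.2. This is an illustration only. It carries office workers over to residents, and it overstates the gap if decay flattens once steps are back at baseline.

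**5. Timing.** The protocol version is dated 28 August 2019. Section 1.1 dates the primary endpoint 26 August and the follow-up 22 September. Counting both days, that is 6 + 22 = 28 days, or four weeks, which fits an active phase that ended at about 26 August. A contrast chosen now may therefore be chosen after the data for it existed.

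**The case against.** The strongest reply is that 4.1 calls this a single-arm pilot, so formal multiplicity control may be more than it needs. That has some force: the inflation in step 3 is modest, and with two contrasts it stays at or below 5%. But the plan states an efficacy objective, hypothesis tests and a power calculation, so it should say which test is the main one.

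Several stronger readings are tempting, and the documents do not support them.

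- **Four tests at 0.05 give an 18.5% error rate** (1 − 0.95⁴). This counts the decline as an efficacy success, counts significant decreases as successes, and treats tests that share data as independent. If all four had to succeed no adjustment would be needed, though the plan does not say that either.
- **The population is undefined.** It is partly settled: the objective and 9.2 point to older adults, and 6.1.1 gives employees largely a supporting role. What is missing is a stated analysis set and the handling of employees.
- **The decline has no window.** The sentence does run from the start to the end of the 8 weeks. The fragment after it may be editing residue, but it should be removed.
- **The contrast was picked after seeing results.** The dates and the past tense in parts of section 6 make this possible. Nothing shows that step data had been examined.
- **The power lost with a last-week primary can be computed from 4.2.** The 2,183-step initial gain and the net decay of 44.8 − 24.3 = 20.5 steps/day are differences from a control group. They are not within-person changes from baseline, which is what a single-arm study estimates.

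**Conclusion.** The concern holds as an internal contradiction with practical consequences. Followed as written, the plan allows any of several contrasts, which its own background leads one to expect will differ, to be reported as the primary result. The textual conflict over follow-up and over the baseline window is certain.

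The numerical effect is less so. A false-claim rate of about 4 to 7% in place of 2.5% assumes an any-increase success rule, two-sided 0.05 for each test (the level appears only in 9.2, without sidedness) and equal correlations between 0 and 0.9. The extra freedom from the open baseline and population is not included, because it depends on day-to-day variability that the documents do not give. The main harm is an undefined primary result; the error inflation is secondary. The change should be made, and it leaves the 42 in 9.2 as it is.

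**What to change.** - **9.1:** name one directional primary contrast within the 8 weeks, consistent with 1.1. For example: in older-adult residents, mean steps/day in the last active week is higher than at baseline, tested at two-sided 0.05, with success only if the change is positive. The 56-day mean would also fit 1.1; choose one.
- **Other hypotheses:** move initial adoption (with its days stated), follow-up, daily decline and the active-versus-Fitbit-only comparison from 1.1 to secondary, or test them in a fixed order after the primary. Delete the stray fragment and state one window for the decline.
- **Baseline:** reconcile 1.1 and 6.1.1 into one window, and say whether days after the kick-off count.
- **9.3:** state that the primary set is the older-adult residents, with employees summarised separately.
- **9.4.2:** replace the broken sentence with one mixed model for repeated measures whose periods match the chosen contrasts. If the 56-day mean or the active-versus-follow-up comparison is used, the model must provide a whole-active-phase mean; first-week and last-week periods alone cannot. Use a separate daily-slope model for the decline.
- **Timing:** date the choice, state whether step data had been seen, and report it as post hoc if so.

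The cost is wording and two standard models, with no new data. Three hypotheses lose primary status, and a last-week primary is harder to meet if steps decay. The documents do not give the within-person change needed to say how much harder.

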9.2 SAMPLE SIZE DETERMINATION

To achieve 80% power to detect a 1,750 step difference in step counts between the pre- and post-intervention periods, with a standard deviation of 2,000 steps and a significance level of 0.05, we are required to enroll at least 42 participants. If we add an additional 25% for possible drop outs, we will need to enroll at least 50 participants into the older adult group.

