4 STUDY DESIGN

4.1 OVERALL DESIGN

This intervention is a single arm, pre-post test pilot study.

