5.5 STRATEGIES FOR RECRUITMENT AND RETENTION

We anticipate screening 110 individuals including women, minorities, and participants across the lifespan, in order to reach the target enrollment size of 100. We anticipate enrolling 100 participants, 50% female and 50% male. We anticipate accruing 75 older adults and 25 adults over 2-weeks.

At the Oaknoll off-site location, word about the study will be spread by word of mouth and advertisements. Advertisements will be displayed on TV monitors throughout Oaknoll. These materials will be distributed by the Activities Coordinator at Oaknoll. The research team members will spread information about the study through word of mouth. Interested participants will contact the Activities Coordinator to schedule a time and location for testing at Oaknoll. She will send out information about the study through Oaknoll's weekly news. If she receives any questions about the research beyond what is included in the brochures, ads, and posters, she will direct the person to contact a member of the research team. Once a participant shows interest in the study from seeing a poster advertisement or ad in the weekly news, she will schedule a time and location for testing at Oaknoll. The eligibly criteria will be listed in the ad, and all potential participants will be screened before the research team goes over the informed consent. Coercion and undue influence will be minimized by informing the subjects that participation in the study is completely voluntary and that they are free to quit the study at any time without penalty.

All participants will receive a Fitbit activity monitor. For compensation, all participants will be allowed to keep the Fitbit activity monitor at the end of the study. Participants who participate in the focus groups will receive a \$50 check for compensation.

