9.4.2 ANALYSIS OF THE PRIMARY ENDPOINT(S)

We will used mixed-effect models to Repeated measures ANOVA.

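### The 42 participants in Section 9.2 match an unpaired two-group formula; a paired pre-post comparison on the same inputs needs at most 23, so the stated 80% power is not this design's power

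*Combined protocol and SAP*

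**What the plan says.** Section 9.2 gives the purpose of the calculation as "To achieve 80% power to detect a 1,750 step difference in step counts between the pre- and post-intervention periods". It takes an SD of 2,000 steps and a significance level of 0.05, and concludes that "we are required to enroll at least 42 participants". The next sentence reads: "If we add an additional 25% for possible drop outs, we will need to enroll at least 50 participants into the older adult group". The section does not name the test or the sidedness. It does not say whether 2,000 is the SD of the within-person change or the SD of step counts in one period, and it gives no pre-post correlation.

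The design and analysis are within-person. Section 4.1: "This intervention is a single arm, pre-post test pilot study". Section 9.4.2 on the primary analysis: "We will used mixed-effect models to Repeated measures ANOVA". Section 9.1 lists four primary hypotheses: a change from "baseline to the initial adoption of the active intervention", a change from baseline to the last intervention week, a change from baseline to follow-up, and a day-by-day decline during the intervention. Section 5.5 on expected recruitment: "We anticipate accruing 75 older adults and 25 adults over 2-weeks".

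**The concern.** In a single-arm pre-post study each participant supplies both measurements, so the sample size depends on the SD of the within-person change. An effect of 1,750 with an SD of 2,000 is large (1,750/2,000 = 0.875), and a paired test of an effect that size needs few people. A requirement of 42 is much higher than expected and suggests a formula for two independent groups.

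If so, the stated 80% describes a comparison this trial does not make. A reader would take the study to be only just adequate for 1,750 steps/day when it can detect a clearly smaller change. Nor could the reader tell which of the four primary hypotheses the figure covers. That matters because Section 9.1 itself expects steps to fall over the intervention, so the early, late and follow-up contrasts may differ in size.

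**Working it through.** **Inputs (Section 9.2).** Difference 1,750; SD 2,000; alpha 0.05; power 80%; stated n = 42; dropout allowance 25%; stated enrolment 50. Two-sided testing is my assumption, with normal quantiles 1.960 and 0.842.

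**1. Reproducing 42.** Unpaired two-group normal formula:

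n per group = 2 x [2,000 x (1.960 + 0.842) / 1,750]² = 20.50, rounded up to 21; total 2 x 21 = **42**.

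The t-based version gives 22 per group (44 in total); the one-sided normal version gives 34 in total.

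**2. Paired calculation on the same inputs.** Normal formula: n = [SD of change x 2.802 / 1,750]². The t-based figures use the noncentral t distribution. If 2,000 is the SD in each period, SD of change = 2,000 x √(2(1 − r)), where r is the pre-post correlation. The documents give no r, so a range is shown.

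| Reading of the SD | SD of change | n, normal | n, paired t |
|---|---|---|---|
| 2,000 is the SD of change | 2,000 | 11 | 13 |
| Per period, r = 0 | 2,828 | 21 | 23 |
| Per period, r = 0.25 | 2,449 | 16 | 18 |
| Per period, r = 0.5 | 2,000 | 11 | 13 |
| Per period, r = 0.8 | 1,265 | 5 | 7 |

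**3. Could something else explain 42?**
- *Multiplicity.* Splitting alpha over four hypotheses (0.05/4 = 0.0125) gives a paired-t n of 18 (SD of change 2,000) or 33 (r = 0).
- *Sidedness.* One-sided testing lowers n: 10 (SD of change 2,000) or 18 (r = 0).
- *Correlation.* For the paired t-test to require 42, the SD of change must be about 3,903 to 3,953. With 2,000 per period, r = 1 − (SD of change/2,000)²/2, which is about −0.90 to −0.95. The normal formula reaches 42 only at about r = −1 (raw 41.006). The documents state no such correlation, and it is implausible for one person's step counts.

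**4. What the trial's numbers deliver (paired t, two-sided 0.05).** The evaluable numbers are the stated 42; 37, from 50 x 0.75 = 37.5; and 56, from 75 x 0.75 = 56.25.

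| Evaluable n | Power for 1,750, r = 0 | Power for 1,750, SD of change 2,000 | Detectable at 80%, r = 0 | Detectable at 80%, SD of change 2,000 |
|---|---|---|---|---|
| 37 | 95.6% | 99.9% | 1,339 | 947 |
| 42 | 97.5% | 99.98% | 1,252 | 886 |
| 56 | – | – | 1,078 | 762 |

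At 42, the detectable change is 1 − 1,252/1,750 = 28% to 1 − 886/1,750 = 49% below the 1,750 stated.

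**5. From 42 to 50.** 42 x 1.25 = 52.5, so 53. 42/0.75 = 56. Neither gives 50. Enrolling 50 and losing 25% leaves about 37, below the section's own 42.

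**The case against.** The plan names no formula, so the unpaired origin is an inference. The match is exact only under the normal approximation, and a sufficiently negative correlation would formally produce 42 from a paired test. Both points stand. The conclusion does not need the origin to be proved: whatever was used, a paired test with a non-negative correlation does not need 42 on these inputs.

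The two cases in the power table are illustrations, not bounds. If 2,000 is the per-period SD and the correlation exceeds 0.5, power is higher and the detectable change smaller. At r = 0.75 the SD of change is 1,414, and at 42 the detectable change is about 886 x 1,414/2,000 = 626. That widens the gap from the stated 80%.

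The paired t-test is also only a stand-in for the mixed model or repeated-measures ANOVA. It does not apply to the fourth hypothesis, a daily decline and not a difference between two periods. This too stands, and is a reason for Section 9.2 to name the contrast it powers.

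The strongest objection concerns weight. The plan says at least 42, the study is a pilot, the error is conservative, and 37, 42 or 75 all exceed 23. So no effect of 1,750 steps is likely to be missed for lack of numbers. That limits the seriousness. It does not make the power statement correct.

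**Conclusion.** The concern holds. The 42 is reproduced exactly by an unpaired two-group calculation. The planned within-person comparison needs 13 (SD of change 2,000) or at most 23 (SD 2,000 per period, correlation zero or above). At 42 evaluable participants the power for 1,750 steps is 97.5% or 99.98% in those two cases, not 80%. These figures assume a two-sided 0.05 paired t-test of baseline against one later period.

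The statement should be corrected before the section is relied on. The error runs in the safe direction and does not put enrolment or the primary comparison at risk. The dropout sentence is separately unreproducible, so the number expected to be evaluable cannot be read from the section.

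**What to change.** Redo Section 9.2 as a paired or repeated-measures calculation. State:
- whether 2,000 is the SD of within-person change or the SD in each period, and in the second case the assumed correlation;
- the sidedness;
- which Section 9.1 contrast is powered;
- the number expected to be evaluable, with dropout arithmetic that links it to planned enrolment and to the 75 older adults in Section 5.5.

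Then give either the power for 1,750 steps or the detectable change at that number. Suggested wording:

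> With [n] evaluable older adults, a [two-sided] 0.05 paired comparison of baseline with [contrast], assuming an SD of within-person change of [x] steps, has 80% power to detect [y] steps/day.

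For n = 37, y is about 947 (x = 2,000) or 1,339 (x = 2,828). For n = 42, y is about 886 or 1,252. For n = 56, y is about 762 or 1,078.

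The cost is a rewrite of Section 9.2. Planned enrolment and data collection do not change.

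### Section 9.2: the enrolment minimum of 50 does not follow from 42 participants and a 25% dropout allowance; it is 53 or 56, depending on what the 25% means

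*Combined protocol and SAP*

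**What the plan says.** The sample-size argument is contained in section 9.2. Its target is "To achieve 80% power to detect a 1,750 step difference in step counts between the pre- and post-intervention periods". The assumed SD is 2,000 steps and the test level is 0.05. From these inputs it concludes that "we are required to enroll at least 42 participants". The next sentence turns that base into an enrolment minimum: "If we add an additional 25% for possible drop outs, we will need to enroll at least 50 participants into the older adult group".

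No other section gives a dropout rate, a rounding rule or a different inflation formula. Section 5.5 gives the expected accrual separately: "We anticipate accruing 75 older adults and 25 adults over 2-weeks".

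**The concern.** Three figures stand in two adjacent sentences (42, 25% and 50), and the third should follow from the first two. It does not, so at least one of them is not what the authors intended. A reader cannot tell whether the study was meant to withstand 25% attrition or only the smaller loss that 50 allows.

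This sentence is the plan's only quantified allowance for attrition. Completion rate is also a planned acceptability measure (section 8.1, Aim 3), so the observed rate may well be compared with the planned allowance. At present the words and the number give different answers to that comparison.

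**Working it through.** **Inputs.** Base 42, allowance 25% and stated minimum 50, all from 9.2; anticipated older adults 75, from 5.5. I take the 42 to refer to the same older adult group as the 50.

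**Is 42 a misprint?** It can be reproduced from the inputs in 9.2 as the total for two independent groups (two-sided 0.05, normal approximation):
- Per group: 2 × (1.960 + 0.842)² × (2,000 / 1,750)² = 20.5, so 21.
- Total: 2 × 21 = 42.

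So 42 looks like a calculated figure and not a slip for 40. Whether that formula suits this design is not examined here.

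**Attempt to reproduce 50 from 42 and 25%.**
- Mark-up (add 25% of the base): 42 × (1 + 0.25) = 52.5, so 53.
- Loss rate (25% of those enrolled are lost): 42 / (1 − 0.25) = 56.

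Neither gives 50. The shortfall is 53 − 50 = 3 or 56 − 50 = 6.

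**What 50 does correspond to.**
- As a mark-up: 50 / 42 = 1.190, an addition of 19%.
- As a loss rate: 1 − 42/50 = 16%, that is, 8 losses among 50.
- A 25% mark-up gives 50 only from a base of 50 / 1.25 = 40, which the plan does not state.
- A 20% mark-up of 42 is 50.4. That becomes 50 only by rounding down, which is the wrong direction for a minimum; rounded up it is 51.

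**Completers if 25% of those enrolled are lost.**

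| Enrolled | Completers | Reaches 42? |
|---|---|---|
| 50 | 50 × 0.75 = 37.5 | No |
| 53 | 53 × 0.75 = 39.75 | No |
| 56 | 56 × 0.75 = 42 | Yes |
| 75 (anticipated, 5.5) | 75 × 0.75 = 56.25 | Yes |

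The second row shows why 53 cannot simply be put in place of 50. It is right for a 25% mark-up but falls short if 25% is the expected loss; 53 preserves 42 completers only up to 11 losses (11/53 = 20.8%).

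**The case against.** The best case on the other side concerns importance, since the arithmetic cannot be rescued.

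- **The gap has no practical effect.** The anticipated 75 older adults exceed the stated minimum by 25, and section 4.1 describes the work this way: "This intervention is a single arm, pre-post test pilot study". This stands, and it keeps the point at low severity.
- **The figure can no longer steer enrolment.** The protocol version is dated 28 August 2019, the synopsis dates the 8-week endpoint 26 August 2019, and section 6.1.1 describes enrolment in the past tense. On those dates recruitment was already over. This also stands: any change corrects the record and should be marked as such.
- **The wording of 9.2 describes an addition, so 53 is the obvious correction.** This stands only in part. An addition is the literal reading, but the stated purpose is to cover dropouts, and for an expected loss rate the figure is 56. The documents do not settle which is meant.

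A reader might go further and infer that the study is underpowered or has to recruit more people. The documents do not support that. Only at the bare minimum of 50, with a full 25% lost, would completers fall below 42; at the anticipated 75 about 56 would remain. A reader might also infer that the mismatch discredits the 42 itself. It does not: the dropout step is wrong whatever the merits of the base, and the suitability of 42 for a single-arm pre-post comparison has to be argued on other grounds.

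**Conclusion.** The figures 42, 25% and 50 in 9.2 are mutually inconsistent, and no convention given in the documents reconciles them. The stated minimum is 3 too low for a mark-up or 6 too low for a loss rate. Put the other way, the words promise an allowance of 25% while the number provides a 19% mark-up, or 16% loss.

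This is a low-severity error in a stated figure. The arithmetic needs no assumption beyond taking the 42 and the 50 to describe the same group. The judgement that nothing practical follows rests on accrual of older adults reaching about the 75 anticipated in 5.5.

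**What to change.** Make one of these edits in 9.2, according to what the authors intended:

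- Keep 50 and state that it allows for 16% dropout (8 of 50) with 42 completers remaining.
- Keep 25%, say that it is a mark-up on the base, and restate the minimum as 53.
- Keep 25%, say that it is the expected loss among those enrolled, and restate the minimum as 56.

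Record the edit as a correction to the stated justification, given the dates in the document; the amendment history in 10.4 is the natural place. The cost is one number or one percentage, plus a few words to say what the percentage means. Section 5.5, the design and the analysis stay as they are.
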